5.2 Analysis of Primary and Secondary Outcomes

The primary outcome, the participant's composite score of tolerability will be constructed using the principal component analysis (PCA) based on 4 GI side effect profile categories (stool consistency, urgency to evacuate, bloating sensation, and flatulence). PCA will be used to account for the expected high inter-patient variability. Comparison of mean tolerability score over 1 week will be with linear mixed models, adjusting for baseline score. Pre-specified covariates are: treatment period and sequence effects from the cross-over design.

The secondary outcome, change in mean stool SCFA over 1 and 4 weeks, will be analyzed using repeated measures of analysis variance (ANOVA) to consider correlation of observations within each participant. Participant and exploratory characteristics will be expressed as mean and standard deviation, median and interquartile range for continuous variables and frequency for categorical variables. Between group comparison of means will also be analyzed using repeated measures ANOVA. Spearman correlations will be used to compare relationships between continuous variables. A P-value of <0.05 will be used for statistical significance.

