2.0 Specific Objectives/ Aims

The primary objective of this study is to determine the feasibility and efficacy of a prebiotic MM to improve metformininduced lower GI side effects in youth with T2D and the secondary objective is to measure the change in stool SCFA content after prebiotic MM intervention.

Aim 1. To compare lower-GI side effects and stool consistency (tolerability score) in youth and young adults with T2D at initiation of daily metformin therapy when used with a daily prebiotic microbiome modulator (MM) vs placebo over a 1-week period.

Hypothesis: A prebiotic MM will be associated with higher tolerability scores (a composite score of lower GI-related side effects and stool consistency) compared to placebo.

Rationale: A prebiotic MM, containing both fiber and polyphenols, reduced metformin-related GI side effects in adults with T2D while retaining, and even augmenting, the hypoglycemic effects expected with metformin therapy in a small study (4). Due to the significant potential for clinical benefit, we propose to validate these results in youth, in whom metformin is the only FDA approved anti-diabetic therapy.

Aim 2. To compare the change in SCFA stool content in youth with T2D on metformin therapy when treated with prebiotic MM vs. placebo after 1 week and 4 weeks.

Hypothesis: The prebiotic MM will be associated with higher SCFA stool content compared to placebo. **Rationale**: SCFAs are microbial metabolites derived from fermentation of dietary fibers that are likely gut mediators of glucose metabolism. Metformin and prebiotic fiber individually have been demonstrated to increase stool SCFA [13, 16, 30, 31]. We propose to further elucidate the mechanism of metformin and MM, both individually and when taken together. **Exploratory aims:** To evaluate the relationship of change in tolerability score with change in stool SCFA, change in gut microbial diversity and SCFA-producing phyla, change in intestinal permeability markers, determine tolerability score for metformin and prebiotic MM over 1 month, and change in measures of glucose, insulin and incretin kinetics after treatment with placebo compared to 4 weeks of continuous prebiotic MM intervention.

[figure not shown]

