2.1 Study Outcomes

Primary Outcome: A composite tolerability score based on 4 GI side effect profile categories over 1 week. **Secondary Outcome**: Stool SCFA content (proprionate and butyrate levels) after 1 week and 4 weeks of treatment. **Exploratory Outcomes**: Stool microbial diversity indices, stool metabolites (bile acid concentrations, lactic acid, hydrogen sulfide), serum markers of intestinal permeability; glucose, insulin, GLP-1 and PYY concentrations during a mixed meal test.

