5.0 Statistical and Power Analyses

5.1 Sample Size Justification

Sample size estimates are based on the mean changes and standard deviations in GI tolerability score observed in the study of adult subjects taking the MM [27] including a mean tolerability score of 7 with standard deviation 4. Using alpha 0.05 with 80% power, we will need 10 participants to complete the study. Assuming a 50% attrition rate for this crossover study, we expect to recruit approximately 20 individuals. For the secondary outcome, our preliminary data reporting a mean change of $2.95\pm3.3 \mu mol/g$ of proprionate and $4.17\pm5.72 \mu mol/g$ of butyrate (Figure 3), 20 participants will achieve 90% power, assuming an α =0.05, and correlation coefficient of 0.5.

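### The SCFA secondary outcome is a level in 2.1 but a change in Aim 2 and 5.2, with no baseline named; whether the stated 90% power applies depends on which is meant

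*Combined protocol and SAP*

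**What the plan says.** Two places describe a level. Section 2.1 gives the secondary outcome as "Stool SCFA content (proprionate and butyrate levels) after 1 week and 4 weeks of treatment", and the Aim 2 hypothesis in 2.0 reads "The prebiotic MM will be associated with higher SCFA stool content compared to placebo".

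Three places describe a change. In 2.0, "the secondary objective is to measure the change in stool SCFA content after prebiotic MM intervention"; Aim 2 is "To compare the change in SCFA stool content in youth with T2D on metformin therapy when treated with prebiotic MM vs. placebo"; and 5.2 states "The secondary outcome, change in mean stool SCFA over 1 and 4 weeks, will be analyzed using repeated measures of analysis variance".

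No section says which stool the change is measured from. Section 5.2 adjusts the primary tolerability score for its baseline but says nothing similar for SCFA. Three samples could serve: the stool from screening, taken before usual metformin is stopped (3.2); the drug-free stool at Visit 2; and the post-washout stool at Visit 4 (Table 1).

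Section 5.1 claims 90% power with 20 participants at alpha 0.05. It starts from a "mean change of $2.95\pm3.3 \mu mol/g$ of proprionate" and 4.17±5.72 µmol/g for butyrate, with a "correlation coefficient of 0.5". It does not say which two quantities are correlated.

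**The concern.** A level and a change are different endpoints, and from the same stools they can give different estimates and P-values. With the definition open, and three possible baselines for the change, the choice could be made after the data are seen. Section 5.1 expects 50% attrition from about 20 recruits, so the comparison is small and sensitive to such a choice.

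Precision is also at stake. In a crossover each participant is already their own control, so subtracting a separate pre-period sample in each period adds the noise of two more stools. That is worthwhile only if the pre-period stool predicts the end-of-period stool well. Here the pre-period stools are drug-free and precede the study meals, while the end-of-period stools follow metformin and a week of provided food, so a high correlation cannot be taken for granted.

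**Working it through.** **Inputs (5.1).** Butyrate: difference 4.17, SD 5.72. Propionate: difference 2.95, SD 3.3. N = 20, correlation 0.5, alpha 0.05. I assume that the ± values are SDs and that the test is two-sided.

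**1. Reproducing the 90%.** For a paired contrast, SD of the difference = SD × √(2(1 − 0.5)) = SD. Normal-approximation power = Φ(difference × √n / SD − 1.96).
- Butyrate: Φ(0.729 × 4.472 − 1.96) = Φ(1.30) = 90.3%. This matches the plan. The paired t gives 87.1%.
- Propionate: Φ(0.894 × 4.472 − 1.96) = Φ(2.04) = 97.9%. The paired t gives 96.6%.

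**2. Level against period-specific change.** Let every stool have SD s and let all four (Visits 2 to 5) share the same correlation ρ.
- Level contrast, V3 − V5: variance 2s²(1 − ρ).
- Change contrast, (V3 − V2) − (V5 − V4): variance 4s²(1 − ρ).

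The ratio is 2. With ρ = 0.5 the butyrate SD rises from 5.72 to 5.72 × √2 = 8.09, and the propionate SD from 3.3 to 4.67. A simulation of the butyrate case gave SDs of 5.72 and 8.08. Power at n = 20 becomes:
- Butyrate: Φ(3.260/1.414 − 1.96) = 63.5% (t: 59.0%).
- Propionate: Φ(3.998/1.414 − 1.96) = 80.7% (t: 76.5%).

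To regain 90%, butyrate would need 40 participants (t: 42) and propionate 27 (t: 29).

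**3. The other reading of 5.1.** Suppose 5.72 is the SD of a change and 0.5 is the correlation between the two periods' changes. The SD of the contrast is again 5.72 × √(2 × 0.5) = 5.72, and butyrate power stays at 90.3% (t: 87.1%). If that correlation is 0.25 or 0, normal-approximation power is 75.9% or 63.5%.

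Steps 2 and 3 use the same SD of change, because 5.72 × √(2(1 − 0.5)) = 5.72. They differ only in how the two changes correlate. Under equal correlation among stools the covariance of the changes is s²(ρ − ρ − ρ + ρ) = 0; step 3 puts the correlation at 0.5.

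**4. Relaxing equal correlation.** Hold every cross-period correlation at 0.5 and let w be the correlation between pre-treatment and end stools in the same period. Relative to the level contrast, the change contrast has variance 4(1 − w). Regressing the end-of-period difference on the baseline difference leaves residual variance 1 − ((w − 0.5)/0.5)².

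| w | Change ÷ level | Covariate ÷ level | Butyrate power for change, n = 20 (z / t) |
|---|---|---|---|
| 0.5 | 2.0 | 1.00 | 63.5% / 59.0% |
| 0.6 | 1.6 | 0.96 | 73.2% / 68.6% |
| 0.75 | 1.0 | 0.75 | 90.3% / 87.1% |
| 0.8 | 0.8 | 0.64 | 95.4% / 93.3% |

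Simple change beats level only when w exceeds 0.75. The covariate form is never above either. With c = (w − 0.5)/0.5, its ratio is 1 − c² = (1 − c)(1 + c), which exceeds neither 1 nor the change ratio 2(1 − c).

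**The case against.** A reader might infer that the change analysis in 5.2 necessarily doubles the variance, so that the 90% in 5.1 is wrong. The documents do not support that, for three reasons.

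First, 5.1 itself starts from a mean change, so the 90% may already be the power for change (step 3). Second, 5.1 does not say what the 0.5 correlates; equal correlation among four stools is a modelling assumption, and the result reverses above w = 0.75. Third, 5.2 does not say that a period-specific sample is subtracted. With Visit 2 as a common baseline, (V3 − V2) − (V5 − V2) = V3 − V5, and the variance ratio is 1.

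All three stand against an unconditional claim, but none of them fixes the definition. The common-baseline reading is strained: Visit 2 to Visit 5 spans 28 to 42 days (7–9 + 14–24 + 7–9, section 3.2), so a 1-week change in Period 2 has to start at Visit 4. The favourable reading of 0.5 needs the two periods' changes to be correlated. A shared response to metformin could produce that, but the pilot data (four youths, one metformin course) cannot estimate it. Even on that reading, the 90% belongs to the change, and the level listed in 2.1 has no stated power.

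It is also fair that the covariate gains nothing over plain level when w = 0.5, and that a fix confined to Visits 3 and 5 would lose the 4-week measure that 2.0, 2.1 and 5.2 all include.

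**Conclusion.** The inconsistency is in the text and does not depend on any assumption: a level in 2.1 and in the Aim 2 hypothesis, a change in the secondary objective, Aim 2 and 5.2, and no baseline named.

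The size of the power loss is conditional. It is about 64% (z) or 59% (t) for butyrate and 81% or 77% for propionate, at n = 20, if period-specific change scores are used and the SDs in 5.1 describe equally correlated levels at 0.5. There is no loss if 0.5 is the correlation between the two periods' changes, or if a common baseline is used. The documents do not settle which applies, so neither the loss nor the 90% can be taken as established.

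This is worth correcting before analysis, although it concerns a secondary outcome in a pilot. Expected attrition lowers power under either definition and is a separate matter.

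**What to change.** - Use one definition of the SCFA outcome in 2.0, 2.1 and 5.2.
- For the 1-week MM versus placebo comparison, analyse propionate and butyrate at Visits 3 and 5, with the same-period pre-treatment value (Visit 2 or Visit 4) as a covariate and not subtracted. Estimate the slope within participants, for example by regressing the end-of-period difference on the baseline difference, which is the form checked above. With the baseline in the model, the treatment estimate is the same whether the response is the level or the change, so this also serves the objective as worded in 2.0.
- State that the screening stool, taken on usual metformin, is not the baseline.
- Keep the 4-week (Visit 6) measure as a separately defined open-label comparison, and name the sample it is compared with.
- In 5.1, say what the 0.5 correlates and whether the SDs are of levels or changes, and restate the power for the chosen definition.

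Cost: changes to wording and a revised power statement. The Visit 2 and Visit 4 stools are already scheduled in Table 1. The model loses one degree of freedom to the covariate.

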3.0 Study Design

3.1 Study Design and Timeline

This 9-week pilot study will have 2 phases and 6 outpatient visits at the NIH Clinical Center (Figure 4). Phase 1 is a 5week randomized double-blind randomized cross-over trial with two 1-week intervention periods (metformin + prebiotic and metformin + placebo). Phase 2 will occur immediately following phase 1 in which participants will start an openlabel 4-week intervention with metformin and the prebiotic MM.

Phase 1: This is a randomized double-blind cross-over study of youth with T2D with two intervention periods (metformin + prebiotic MM BiomeBliss® ®, and metformin + placebo). Participants will have 5 study visits over the 5-week period. After screening history and physical examination are performed at visit 1, participants will enter a 1-week run-in period in which metformin therapy will be discontinued and blood glucose will be monitored twice daily via finger stick or with a continuous glucose monitor. The order of intervention will be randomized at Visit 2; when initiating metformin, participants will have 1-3 days of dose escalation, then arrive at a final dose of 850mg twice daily. After 7-9 days of treatment, participants will be evaluated as described in Table 1, then enter a 2-week washout period of prebiotic/placebo and metformin, and then cross over to the opposite intervention for 1 week.

Phase 2: This is an open-label 4-week extension of metformin + prebiotic MM. Participants will receive a 1-month supply of metformin and prebiotic at the end of Phase 1 (Visit 5) and be evaluated for measures of stool metabolite and glycemia at the end of the trial (Visit 6).

Every effort will be made to adhere to the proposed timelines, but some flexibility is required for scheduling of other studies, unanticipated equipment maintenance, etc. Scheduling variations will not be reported.

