4.2 Short Chain Fatty Acid Analysis

Fecal samples will be grounded with a pellet pestle motor, followed by being resuspended in 1 mL PBS buffer (0.1 M, pH 7.4). After 4 h dissolution with 1 min vortex every 20 min, samples will be centrifuged (12, 000 g, 10 min) and passed through the 0.45 μ m membrane filter. Cell-free samples were used for determining the concentrations of SCFA (lactate, acetate, propionate and butyrate) using a high-performance liquid chromatography (Waters-2695 Alliance HPLC system, Waters Corporation, Milford, MA, USA) with DAD detector at 210 nm, equipped with a Aminex HPX-87H column (Bio-Rad Laboratories, Hercules, CA). Sample (10 μ L) will be injected each time and H₂SO₄ (0.005 N) will be used to elute the column with a flow rate of 0.6 mL/min at 35°C.

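### Aim 2 has two acids at two times under one P<0.05 rule, with no deciding acid, time or contrast named; the uncontrolled 4-week values should not be able to decide it

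*Combined protocol and SAP*

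**What the plan says.** Section 2.0 gives Aim 2 a single hypothesis: "The prebiotic MM will be associated with higher SCFA stool content compared to placebo". The aim itself asks for the comparison "when treated with prebiotic MM vs. placebo after 1 week and 4 weeks". Section 2.1 defines the secondary outcome as "Stool SCFA content (proprionate and butyrate levels) after 1 week and 4 weeks of treatment", which makes up to 2 × 2 = 4 readings of that hypothesis.

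For the analysis, section 5.2 states "change in mean stool SCFA over 1 and 4 weeks, will be analyzed using repeated measures of analysis variance (ANOVA". It does not say whether this means one model per acid, a combined measure, an overall test, or separate contrasts at each time. The section closes with "A P-value of <0.05 will be used for statistical significance", and no adjustment or order of testing appears anywhere.

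Two other places bear on this. Section 4.2 assays four analytes under the SCFA name, "determining the concentrations of SCFA (lactate, acetate, propionate and butyrate", so a mean SCFA is not defined. Section 3.1 describes the source of the 4-week values: "This is an open-label 4-week extension of metformin + prebiotic MM".

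**The concern.** Aim 2 is the trial's only secondary aim, and section 5.1 gives it a power statement, so readers will expect a yes or no. The plan does not say which result gives that answer. Depending on how the ANOVA is read, Aim 2 could rest on one, two or four tests, and that choice could be made after the data are seen. The error rate attached to a positive claim would then depend on the choice.

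The two times also differ in kind. The 1-week comparison is randomised and blinded within participants. Everyone receives open-label MM in Phase 2, so a 4-week comparison with placebo would have to reuse the 1-week placebo value. Any effect of calendar time, longer metformin exposure or diet would be mixed with the effect of MM. Table 1 shows metabolic-kitchen meals given only at Visits 2 and 4, so the 4-week phase does not share the standardised diet.

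**Working it through.** **Inputs.** From 5.1: propionate change 2.95 (SD 3.3) and butyrate change 4.17 (SD 5.72) µmol/g; 20 participants; alpha 0.05; correlation 0.5; 50% attrition, hence 10 completers. The documents do not state sidedness (taken as two-sided) or the correlation between the acids (varied from 0 to 0.9).

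**The plan's own figure.** For a paired comparison with correlation 0.5, the SD of the difference is SD × √(2(1 − 0.5)) = SD. The effect sizes are therefore 2.95/3.3 = 0.89 and 4.17/5.72 = 0.73.
- Normal approximation at n = 20: butyrate, Φ(0.729 × √20 − 1.96) = Φ(1.30) = 90.3%; propionate, 97.9%. The stated 90% is reproduced by butyrate.
- Noncentral t: 87.1% and 96.6%.

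**Error rate with four separate two-sided 0.05 tests.**
- Independent, either direction: 1 − 0.95⁴ = 18.5%.
- Independent, hypothesised direction only: 1 − 0.975⁴ = 9.6%. One two-sided test gives 2.5% in that direction.

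The tests are not independent. If the 1-week and 4-week differences share one placebo value and all values have equal variance and equal correlation, the two differences correlate 0.5. Simulated paired t tests at n = 10 with that structure give:

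| Correlation between acids | Any P<0.05, either direction | Any P<0.05, higher SCFA |
|---|---|---|
| 0 | 17.7% | 9.2% |
| 0.5 | 16.7% | 8.5% |
| 0.7 | 15.6% | 7.8% |
| 0.9 | 13.3% | 6.8% |

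The multivariate normal version gives 17.4% down to 12.7%, and 8.9% down to 6.3%. With the independent case as the upper end, the ranges are about 13-18.5% and 6-10%. If the times correlated 0.7 as well as the acids 0.9, the figures would be 11.6% and 5.8%.

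**Error rate under the other readings, either direction.**
- One test per acid: 1 − 0.95² = 9.75% if independent, 9.1% at correlation 0.5, about 7% at 0.9.
- One test on a single mean SCFA: 5%.

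**Power of candidate deciding tests at 10 pairs (paired t, two-sided 0.05).**
- Propionate 71%; butyrate 54%.
- Sum of the two: mean 2.95 + 4.17 = 7.12; SD = √(3.3² + 5.72² + 2ρ × 3.3 × 5.72). For ρ = 0, 0.5 and 1 the SD is 6.60, 7.90 and 9.02, the effect size 1.08, 0.90 and 0.79, and the power 86%, 72% and 60%.
- The sum has propionate's effect size when its SD is 7.12/0.894 = 7.96, which solves to ρ of about 0.53. Above that it has less power than propionate alone.
- Holm's first step (0.025): propionate 57%, butyrate 40%. The chance that at least one acid succeeds is about 68% at ρ = 0.5 and 64% at ρ = 0.7.

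**The case against.** The best defence is that this is a pilot with one primary outcome that has its own model, and that the other outcomes are labelled secondary or exploratory. That stands for the primary outcome, which this point does not touch. It does not settle Aim 2, which has a hypothesis, a power statement and a significance rule.

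The second defence is that repeated measures ANOVA need not mean four tests. This is correct. The four-test figures describe one permitted reading, and the defect is that the plan does not choose.

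Three stronger readings are tempting, and the documents do not support them.
- A reader might infer that Aim 2 would be declared positive by chance in 16-18% of trials. That counts significantly lower SCFA, which contradicts the hypothesis, and it takes four tests and a low to moderate acid correlation as given.
- A reader might infer a 40-54% chance of a false exploratory finding. That needs 10 to 15 independent tests. The plan states no such count, several of the outcomes come from the same meal test, and sections 2.0 and 2.1 already label them exploratory.
- A reader might infer that naming the sum of the two acids costs no power. That fails once the acids correlate above about 0.53.

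**Conclusion.** The point holds as a gap in the decision rule for Aim 2. Depending on the reading, the chance of at least one P<0.05 under the null runs from 5% to about 18.5% in either direction. With four separate tests it is about 6-10% in the hypothesised direction, roughly 2.5 to 4 times the 2.5% of a single test. These figures rest on two-sided testing, an assumed acid correlation of 0 to 0.9, and a correlation between times of no more than about 0.5.

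Separately from any alpha arithmetic, the 4-week comparison has no concurrent placebo and should not be a route to a positive Aim 2. It would be a worthwhile clarification of the plan. The primary conclusion does not depend on it.

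**What to change.** In section 5.2, state that Aim 2 is decided by the randomised 1-week MM-minus-placebo contrast on one named SCFA measure, two-sided 0.05. The measure may be one acid, or propionate plus butyrate, and must be fixed before unblinding. If both acids must count, use Holm across the two 1-week tests. Report the 4-week values, the remaining SCFA measures, the exploratory outcomes and the Spearman correlations with 95% CIs and nominal P-values. Replace the general significance sentence so that it covers only the primary test and the named Aim 2 test or tests.

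The change is wording only: no new data, visits or participants. The cost is that fewer results can be called significant. The choice of measure is a trade-off, and no option is best at every acid correlation. At 10 completers, the single-test options have 71% (propionate), 54% (butyrate) or 60-86% (sum) power, and Holm's first step lowers the separate acids to 57% and 40%. All of these use the section 5.1 inputs, which come from four youths before and after metformin, not from MM versus placebo, so they are only a rough guide to the choice.

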6.0 Collection and Storage of Human Specimens or Data

6.1 Research Use, Storage and Disposition of Human Subjects' Samples

For future reference and potential use, we will store all samples collected in this protocol in our locked freezers for an unlimited period of time. Samples will be labeled with coded identifiers linked to patient identity only via a secured database. Research records and data with personal identifiers will be stored in our locked offices, the medical record department, and the electronic study database. This material will additionally be protected by medical record and computer access procedures. Access to records and data associated with personal information will be restricted to the Principal Investigator, Co-Investigators, study support staff, study monitors and database support staff.

Subjects may request that unused samples be removed from our freezers and be destroyed. If no such request is made, we will keep samples until they are completely used or no longer of scientific value, at which time they will be destroyed. We do not plan to destroy personal medical information or stored data. The Principal Investigator will report loss or destruction of data or samples to the IRB.

